4.2 Standard Reporting Conventions

Tables, listings, and figures will be prepared in accordance with the current International Conference on Harmonization Guidelines. The information and explanatory notes in the “footer” or bottom of each table and listing will include the following information:

- Date of output generation
- SAS® program name, including the path that generates the output
- Any other output specific details that require further elaboration

All hypothesis tests and confidence intervals will be two-sided at an alpha level of 5%.

Version 9.1 or higher of the SAS system will be used to analyze the data, as well as to generate tables, figures, and listings.

In general, tables will be formatted with a column displaying findings for all subjects combined. The summary tables will clearly indicate the number of subjects to which the data apply and unknown or not performed are distinguished from missing data.

The treatment groups will be referred to in the tables, listings, and figures with the following conventions:

- Intepirdine 35 mg
- Placebo

Data analyses will be performed by, or under the direct supervision of, Axovant Sciences.

Efficacy and safety measures over the course of the study will be presented. Continuous data will be summarized by means, SDs, medians, maximum, minimum, and number of subjects. Categorical data will be summarized by counts and percentages.

Data collected in the CRF, as well as laboratory data, will be provided in data listings, sorted (in general) by sequence, subject, period, and date. For date fields, Day on Treatment will be calculated and presented in these listings.

Deviations from the analyses as described in this SAP will be identified in the final Clinical Study Report. When differences exist between the protocol-described analysis and the SAP, the SAP will take precedence.

4.3 Handling of Missing Data

Unless otherwise specified, all data will be evaluated as observed, and no imputation method for missing values will be used.

Where necessary for the calculation of derived variables, partial dates will be completed using the earliest calendar date based on the partial date provided. This rule is valid for all partial dates with the exception of the following:

- Start and stop dates of adverse events
- Start and stop dates of concomitant medication

Completely missing dates will not be replaced and the corresponding derived variables will be set to missing.

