4.1.5 Visits and Periods

There are 5 study periods during this study:

- The Screening Period is defined as the period of time prior to the subject receiving the first dose of single-blind placebo run-in medication.
- The Single-Blind Placebo Run-In Period (Period I) is defined as the period from the first dose of single-blind run-in medication and ends on the last dose date of single-blind run-in medication. The assessments taken on the date of the first dose of randomized double-blind investigational product will be assumed to have been completed before the first dose of double-blind investigational product and will be slotted to this period.
- The First Two-Week Double-Blind Treatment Period (Period II) starts on the date of first dose of double-blind investigational product and ends on the last dose date. If the first dose of randomized investigational product is taken on the same day as Visit 3 assessments, it will be assumed that the assessments were completed before the first dose of double-blind investigational product has been taken.
- The Single-Blind Placebo Washout Period (Period III) starts one day after the last dose of the double-blind medication has been taken in Period II and lasts until the first dose of the double-blind investigational product in Period IV. The assessments taken on the date of the first dose of randomized double-blind investigational product will be assumed to have been completed before the first dose of double-blind investigational product and will be slotted to this period.
- The Second Two-Week Double-Blind Treatment Period (Period IV) starts on the date of the first dose of double-blind investigational product and ends on the last dose date. If the first dose of randomized investigational product is taken on the same day as Visit 5 assessments, it will be assumed that the assessments were completed before the first dose of double-blind investigational product has been taken.

A safety follow-up telephone call will be conducted approximately 2 weeks after completion of Period IV.

Study visits will be determined from the scheduled times as reported on the CRF. As indicated in Table 1, Schedule of Assessments visit windows of +/- 3 days are allowed for scheduling purposes. For analysis purposes in this crossover study, no visit reassignment will be used even if a visit falls before or after the scheduling window.

Table 1: Schedule of Events

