5.8 Extent of Treatment Exposure

Duration of exposure for the Double-Blind Treatment Period (Period II and Period IV) will be calculated by treatment group as follows:

- Duration of exposure in days = (Double-Blind Treatment Period stop date – Double-Blind Treatment Period start date) + 1

Duration of exposure will be tabulated descriptively and categorized as:

- 0 to 1 week
- >1 to 2 weeks
- >2 weeks

Note: Duration of exposure will exclude any dates with documented dose interruptions.

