5.9 Treatment Compliance

Compliance with study drug will be assessed during the run-in and over the Double-Blind Treatment Periods (Period II and Period IV) using drug dispensing records. Treatment compliance during the double-blind period will be computed by determining the number of tablets taken relative to the number of tablets expected. Subjects are expected to take one tablet per day of each.

Treatment compliance based on the drug accountability per subject/period will be calculated as follows:

- Compliance (%) = (number of tablets taken in the period)/(number of tablets expected)*100

- Number of tablets taken = the number of tablets dispensed in the period – the number of tablets returned
- Number of tablets expected = (date of the last dose - date of the first dose + 1 in the period)

Summary of treatment compliance will be presented by treatment group. The number and percentage for compliance expressed as a categorical variable (<80%, ≥80% to ≤120%, and >120%) will also be presented by treatment group.

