7.1 Adverse Events

Adverse events will be classified using the MedDRA version 18.1 coding dictionary. Tabulations will include an overall incidence of at least one adverse event, incidence within system organ class (SOC), and incidence by preferred term. Each subject may only contribute once per treatment group, that is by first occurrence to each of the incidence rates, regardless of the number of occurrences, as follows:

- Adverse events occurring prior to the first dose of double-blind investigational product will be referred to as Treatment-Emergent AEs (TEAEs) and presented as Placebo Run-In events.
- Adverse events occurring on or after the first dose of each double-blind two-week treatment period (Period II and period IV), and within 7 days of the last dose of double-blind investigational product, will be referred to as TEAEs and presented by treatment group.
- Events occurring 7 days after the last dose of Period II and Period IV and for the post-treatment Follow-up Period starting at day 8 (up to 14 days post-last-dose) will be presented as Post-Treatment Period. These events will only be included in a data listing.

Tabulations of the incidence of AEs will be presented as follows:

- Overview of TEAE
- TEAE by SOC and preferred term
- TEAE by preferred term
- TEAE by SOC, preferred term, and relationship to study drug
- TEAE by SOC, preferred term, and maximum severity (mild, moderate, and severe)

All AEs will be listed with its relationship to study drug and severity, flagging those which are not events during treatment-emergent period.

A listing of all deaths and serious AEs will be provided. Any TEAE leading to study drug temporary and permanent discontinuation will also be listed.

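### SAP 4.3's earliest-date rule also covers a partial last-dose date, giving non-positive exposure or an early-closing treatment-emergent window in the probably few subjects affected (minor)

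*SAP*

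**What the plan says.** SAP 4.3 gives one general rule for dates that a derived variable needs: "partial dates will be completed using the earliest calendar date based on the partial date provided". On scope it says "This rule is valid for all partial dates with the exception of the following", and the two exceptions are start and stop dates of adverse events and of concomitant medication. For dates with no information at all it says "Completely missing dates will not be replaced and the corresponding derived variables will be set to missing". The SAP has no separate rule for study-drug dosing dates and no floor at the first dose.

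The last-dose date feeds several derived quantities:

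- **Period end (SAP 4.1.5).** A double-blind period "starts on the date of first dose of double-blind investigational product and ends on the last dose date".
- **Exposure (SAP 5.8).** "Duration of exposure in days = (Double-Blind Treatment Period stop date", minus the start date, plus 1.
- **Compliance (SAP 5.9).** The denominator is "Number of tablets expected = (date of the last dose - date of the first dose + 1 in the period".
- **Treatment-emergent events (SAP 7.1).** Events from the first dose of a period and "within 7 days of the last dose of double-blind investigational product" are tabulated by treatment. Later events go to a listing only.
- **Laboratory and ECG summaries (SAP 7.2, 7.4).** Potentially clinically significant values, laboratory shifts and QTcF categories use the double-blind periods plus 7 days.

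For adverse event and medication end dates with the day missing, SAP 4.3.1 goes the other way and takes the last day of the month.

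**The concern.** Completing a date with its earliest possible value is a common convention for start dates. Applied to a stop date, it shortens the interval. Here the interval is only about two weeks, so moving the stop date back to the first of the month can put it before treatment began.

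Exposure and expected tablets would then be impossible values. The treatment-emergent window would close while the subject was still taking study drug, and on-treatment events after that point would leave the by-treatment tables. Safety is the trial's secondary objective and only about 30 to 40 subjects are planned, so one misplaced event can show in a table. A partly known date also fares worse than an unknown one: it gives a wrong value, where a completely missing date gives a missing value.

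**Working it through.** The documents state no figure on this point, so there is nothing to reproduce. The check follows the SAP's own definitions.

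**Inputs**
- Period length L, one tablet a day: nominally 14 doses. The visit window of ±3 days (Protocol 8.1) gives 11 to 17.
- First dose: taken in clinic (Protocol 7.1), so taken as known.
- Last dose: month and year known, day missing. SAP 4.3 sets it to the 1st of that month.
- Assumption: start dates spread evenly over a 365-day year.

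**Formulas.** Let D be the true day of the month of the last dose. Imputation moves the date back by D − 1 days.
- Exposure (5.8) and expected tablets (5.9) = L − (D − 1) = L + 1 − D.
- The treatment-emergent window (7.1) closes on the 8th of the month (1st + 7 days).

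**Results for L = 14** (exposure = 15 − D)
- Exposure of zero or less needs D ≥ 15. Each month has 14 days with D ≤ 14, so the share is (365 − 12 × 14)/365 = 197/365 = 54.0%.
- The mean of D over the year is 5738/365 = 15.7, so mean imputed exposure is 15 − 15.7 = −0.7 days against a true 14.
- The window closes before the true last dose when D ≥ 9: (365 − 12 × 8)/365 = 269/365 = 73.7%. This does not depend on L.
- The window closes before the first dose when D ≥ 22: (365 − 12 × 21)/365 = 113/365 = 31.0%.
- The true window is 14 + 7 = 21 days. The days lost are the smaller of D − 1 and 21, with mean 4893/365 = 13.4 days, or 64% of 21.

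**Range over period length.** The share with exposure of zero or less is (365 − 12L)/365:

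| L (days) | Share |
|---|---|
| 11 | 233/365 = 64% |
| 14 | 197/365 = 54% |
| 16 | 173/365 = 47% |
| 17 | 161/365 = 44% |

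Enumerating every start date over three calendar years, one of them a leap year, gives the same rounded values.

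**Day and month both missing** (date set to 1 January, L = 14): exposure is zero or less for 351/365 = 96.2%, and the window closes on drug for 357/365 = 97.8%.

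**Example.** First dose 10 May; true last dose 23 May, recorded only as May; 14 tablets taken. The imputed last dose is 1 May.
- Exposure = 1 − 10 + 1 = −8 days, which fits no category in 5.8.
- Compliance = 14/(−8) = −175%, which falls in the below-80% category of 5.9 although every tablet was taken.
- The window closes on 8 May, two days before dosing began.

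**The case against.** The strongest reply is that the trigger will seldom occur, and most of that reply stands. Protocol 7.1 has the Visit 4 bottle started in clinic, so for a subject who reaches Visit 4 the end of Period II is bounded by a known date. Drug accountability is checked at Visits 3 to 6. Protocol 7.6 requires returned tablets to be reconciled, and it reschedules the visit if a double-blind dose was missed in the two days before gait testing, so sites must establish recent dosing. Protocol 11.1.5 makes the start and end dates of investigational product required source data. A last dose known only to the month would normally raise a data query.

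The consequence is also partly contained. Negative exposure is conspicuous. SAP 7.1 lists all adverse events, flags those outside the treatment-emergent period, and lists deaths and serious events. The safety analysis is descriptive.

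A reader might infer that last doses, being mostly taken at home, are the dosing dates most likely to be partial, and that subjects who stop early because of an adverse event are hit most. The arithmetic does give a higher share for shorter treatment, but nothing in the documents shows that early stoppers more often have partial dates. Protocol 6.6.2 asks for an early termination visit, preferably within 7 days of stopping. For a subject lost to follow-up whose date is wholly missing, 4.3 sets the derived variables to missing, so this mechanism does not arise.

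What the reply does not remove is the rule itself. It covers last-dose dates by its own terms, and it gives a wrong answer whenever it is applied to one, except when the true last dose fell on the first day of the imputed interval.

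**Conclusion.** Wrong as written; minor. Given a last-dose date with only the day missing, exposure and expected tablets are zero or negative in about 54% of cases at 14 days (64% to 44% over 11 to 17 days). The treatment-emergent window closes before the true last dose in about 74%. The 7-day extensions for laboratory and ECG summaries are displaced in the same way.

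These shares rest on evenly spread start dates and daily dosing. They are conditional on a partial date and must not be read as expected effects on the trial. The number of partial last-dose dates is not given and is probably small.

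Nor do the documents support reading this as a threat to the efficacy result. The gait model in SAP 6.3.2 does not use the last-dose date, and SAP 4.1.5 takes visits as recorded without reassignment.

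**What to change.** Before unblinding, add study-drug last-dose dates to the exceptions in SAP 4.3, with this rule: a partial last-dose date is completed with the latest date compatible with the recorded part, subject to two limits.

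- **Cap:** the day before the first dose from the next bottle (Period II), or the Visit 6, early termination or last-contact date, whichever applies and is earliest.
- **Floor:** never before the first dose of that period.

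In the example, with the next bottle started on 24 May, the completed date is 23 May, exposure is 14 days and the window closes on 30 May.

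The cost is about one sentence in the SAP and a small change to the derivation code. The downside is that exposure, and with it the safety window, may be overstated by some days in an affected subject. Other conventions are possible; what matters is that the direction suits a stop date and that the rule is fixed in advance.

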#### **8.3.2.1.5. Method of Detecting Adverse Events and Serious Adverse Events**

Care will be taken not to introduce bias when detecting AEs and/or SAEs. Open-ended and non-leading verbal questioning is the preferred method to inquire about AE occurrence.

Appropriate questions include:

- “How are you feeling?”
- “Have you had any (other) medical problems since your last visit/contact?”
- “Have you taken any new medicines, other than those provided in this study, since your last visit/contact?”

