4.3.1 Incomplete Dates for Concomitant Medication and Adverse Events

For analyses of AEs and concomitant medication usage, a complete date must be established in order to correctly identify the AE or medication as occurring during treatment or not. For purposes of imputing missing components of partially-reported start and stop dates for AEs and for medication use, the algorithms listed below will be followed. Start and stop dates of AEs or concomitant medication will be displayed as reported in the subject data listings (ie, no imputed values will be displayed in data listings).

Missing start day, but month and year present:

- If the occurrence of the AE/concomitant medication is in the same month and year as is the date of first dose of investigational product in Period II (which is the first Two-Week Double-Blind Treatment Period), then the start day of the event/concomitant medication will be assigned to the day of the first dose of investigational product taken in Period II.
- If the occurrence of the AE/concomitant medication is in the same month and year as is the date of the first dose of investigational product in period IV (which is the second Two-Week Double-Blind Treatment Period), then the start day of the event/concomitant medication will be assigned to the day of the first dose of investigational product taken in Period IV.
- If the dates of first dose of investigational product for Period II and for Period IV fall in the same month, then the start date day of the event/concomitant medication will be assigned to the day of the first dose of investigational product taken in Period II.
- Otherwise, the start day will be set to the 1st day of the month.

Missing start day and month, but year present:

- If the occurrence of the AE/concomitant medication is in the same year as is the date of first dose of investigational product in Period II (which is the first Two-Week Double-Blind Treatment Period), then the start day of the event/concomitant medication will be assigned to the day of the first dose of investigational product taken in Period II.
- If the occurrence of the AE/concomitant medication is in the same year as is the date of the first dose of investigational product in period IV (which is the second Two-Week

Double-Blind Treatment Period), then the start day of the event/concomitant medication will be assigned to the day of the first dose of investigational product taken in Period IV.

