5.7 Prior and Concomitant Medications

Prior and concomitant medication verbatim text will be coded using the World Health Organization's Drug Dictionary (WHO-DD), and will be classified according to the default Anatomical Therapeutic Chemical (ATC) classification system code, WHO-DD Drug Name, and preferred term.

Medications will be tabulated as:

- Prior medications
- Concomitant medications
 - Single-blind run-in and washout periods
 - Double-blind periods

Medications received prior to the date of first dose of single-blind investigational product are considered as prior medications. Medications will be considered as concomitant if the start date of the medication is on or after the date of first intake of investigational product or if the start date is prior to the first date of investigational product, but the medication is ongoing during the treatment period in the study.

Concomitant medications will be further split by concomitant medications taken during the Single-Blind Placebo Run-In Periods and concomitant medications taken during the Double-Blind Treatment Periods. Those will be presented by treatment group. It should be noted that a concomitant medication can be counted in more than one period.

Use of non-investigational products will be summarized (number and percentage of subjects) by treatment, the highest ATC class level, and preferred term for the safety population.

A listing of non-medication therapy will be provided.

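### An adverse event with no start date at all has no place in the SAP's by-treatment TEAE tables, so incidence on either treatment can be understated

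*SAP*

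**What the plan says.** SAP 4.3 completes partial dates with the earliest possible calendar date, but exempts the start and stop dates of AEs and concomitant medications. The sentence that follows carries no exemption: "Completely missing dates will not be replaced and the corresponding derived variables will be set to missing".

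SAP 4.3.1 gives the separate rules for AEs and medications. It states the need plainly: "a complete date must be established in order to correctly identify the AE or medication as occurring during treatment or not". Its algorithms are for "imputing missing components of partially-reported start and stop dates for AEs and for medication use". The least complete start date with a rule is "Missing start day and month, but year present".

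SAP 7.1 sorts AEs by onset relative to double-blind dosing. Those from the first dose of Period II or IV to 7 days after the last dose "will be referred to as TEAEs and presented by treatment group". Earlier events go to the placebo run-in and later ones are listed only. All five incidence tabulations in that section are TEAE tables. All AEs are also listed, as are all deaths and serious AEs.

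For medications, SAP 5.7 sets its test against study drug: "Medications will be considered as concomitant if the start date of the medication is on or after the date of first intake". A drug begun earlier and still being taken during treatment also qualifies.

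**The concern.** The SAP requires a complete date in order to classify an AE, yet its default leaves the least complete records without one. In this crossover the onset date decides both whether an event is treatment-emergent and which treatment it belongs to. Protocol 10.4.1.1 assigns AEs by the last dose received, which needs the onset date too. An event without one can only drop out of the tables, which is the non-conservative direction for safety.

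Safety and tolerability is the only secondary objective, and SAP 7 makes the safety analysis descriptive, so the tabulated counts are the result. The subjects have dementia and caregivers report on their status, so an unknown onset date is plausible. The information needed to place such an event should usually exist: AEs are reviewed at every visit, and Protocol 8.3.2.1.5 gives as a suitable question "Have you had any (other) medical problems since your last visit/contact".

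**Working it through.** The plan states no figure on this point, so there is none to reproduce. The check is a trace of the rules, then an illustration of size.

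**1. Trace by completeness of the AE start date**

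| Start date recorded | Governing rule | Date assigned | Place in the TEAE tables |
|---|---|---|---|
| Month and year | SAP 4.3.1 | First dose of Period II or IV if that month matches; otherwise the 1st of the month | Classified |
| Year only, a dosing year | SAP 4.3.1 | First double-blind dose in that year (Period II if both fall in it) | Counted as treatment-emergent |
| Nothing | SAP 4.3 default | None; derived variables missing | None defined |

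Participation lasts about 14 weeks (Protocol Summary), so a bare year says almost nothing about the period. The last two rows hold nearly the same information and are treated in opposite ways.

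**2. One subject lost from a row**

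The change is 1/N. The planned sample is 30 to 40 (SAP 1.3).

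- N = 30: 1/30 = 3.3 points. N = 40: 1/40 = 2.5 points.
- SAP 7 also tabulates safety by dementia type, with about 15 to 20 subjects each: 1/15 = 6.7 points, 1/20 = 5.0 points.

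**3. Effect on the comparison**

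Let p be the true incidence on a treatment and m the share of AEs with no start date. With one AE per affected subject and the same m on both treatments, observed incidence = p(1 − m). Neither p nor m is in the documents; I assume p of 20% to 40% and m of 0 to 10%.

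| True p, intepirdine / placebo | m | Observed | Difference | Ratio |
|---|---|---|---|---|
| 30% / 30% | 2% | 29.4% / 29.4% | 0 | 1.00 |
| 30% / 30% | 5% | 28.5% / 28.5% | 0 | 1.00 |
| 30% / 30% | 10% | 27.0% / 27.0% | 0 | 1.00 |
| 40% / 20% | 10% | 36% / 18% | 18 points (true 20) | 2.00 |
| 20% / 40% | 10% | 18% / 36% | −18 points (true −20) | 0.50 |

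At p = 30% and m = 10% the expected loss per treatment column is 30 × 0.30 × 0.10 = 0.9 subjects, or 40 × 0.30 × 0.10 = 1.2. At m = 0 there is no effect.

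**4. Subjects with several AEs**

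SAP 7.1 counts each subject once per treatment group in each rate. A subject with k AEs on a treatment leaves the any-TEAE row only if all k are undated. If dates go missing independently, that has probability m^k: at m = 10%, 10% for k = 1, 1% for k = 2 and 0.1% for k = 3.

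**The case against.** The strongest reply is that the case hardly arises. Even the year must be unknown, yet AEs are reviewed about every two weeks during treatment. Protocol 11.1.5 requires AE start and end dates in source records, Section 9 provides for data cleaning, and Section 11.3.1 has the monitor check completeness. This stands as an argument about size: the documents give no sign that such events will be common. It does not close the gap, since the SAP itself provides for completely missing dates and the outcome it sets is exclusion.

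A second reply is that the SAP never says these events are excluded and does not name the treatment-emergent flag among its derived variables. That is correct; exclusion is an inference. But TEAE status and treatment column are derived from onset timing, and SAP 7.1 offers an undated event no other place in its tables.

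Three stronger readings are tempting, and the documents do not support them.

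- A reader might infer that intepirdine's rates in particular are understated. The rule is blind to treatment and works alike in both periods and both sequences. With equal missingness the ratio is unchanged.
- A reader might set the loss beside the falls figures in Protocol 3.1.1, 2% against 6%, a difference of 4 points. One subject, at 2.5 to 3.3 points, does not reach that, and those figures come from a 48-week study, not two-week periods.
- A reader might infer that serious events disappear. SAP 7.1 lists all deaths and serious AEs, dated or not.

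For medications, SAP 5.7 defines prior use by receipt before the first single-blind dose, so an undated background drug can still be classed as prior. Only its concomitant status is left open, and that has no bearing on AE rates.

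**Conclusion.** The gap is real and modest. Followed as written, SAP 4.3 and 4.3.1 leave a wholly undated AE in no treatment column, while a nearly identical year-only record is counted. Incidence on either treatment can be understated, by 2.5 to 3.3 points per subject lost from a row in the full sample. A true difference between treatments shrinks slightly in absolute terms.

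Any effect requires that such events occur, that they truly began on treatment (AEs are collected from consent), and that the subject has no dated event in the same row. The number is not known from the documents and may be small or zero. The efficacy analysis is untouched. The point is worth settling because the correction is nearly free and, made before unblinding, avoids case-by-case decisions later.

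**What to change.** Add a branch to SAP 4.3.1 for an AE with a completely missing start date. Unless its stop date shows otherwise, classify it by the visit at which it was first reported:

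- At or before Visit 3: run-in or earlier.
- After Visit 3 and up to Visit 4: Period II treatment.
- After Visit 5 and up to Visit 6: Period IV treatment.
- At Visit 5, Visit 7 or early termination: treatment-emergent on the preceding double-blind treatment, and flagged, because onset within the SAP's 7-day window cannot be ruled out.
- Reporting visit unknown: list and count separately. Do not assign these to intepirdine by default, which would replace a treatment-neutral rule with a one-sided one.

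Report how many events were handled under each branch. Confirm that the visit of first report can be recovered from the case report form or its audit trail; the documents do not say that it is a collected field.

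For medications, state that a drug with no start date counts as concomitant in every period its stop date does not rule out. This changes only the medication summaries.

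The cost is a few sentences and a few lines of code. The downside is that some events may be counted as treatment-emergent when they were not, chiefly those first reported at Visit 5 or Visit 7; the flag lets a reader see them.
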